1. Study Summary

Project Title	Biomarker-Based Approaches to Understand and Predict Cardiovascular Toxicity from Androgen Deprivation Therapy Targeting the Gonadotropin Releasing Hormone Pathway in Prostate Cancer Men
Project Design	Open-label randomized clinical trial with parallel prospective cohort study
Primary Objective	Elucidating the pathophysiologic link between gonadotropin releasing hormone agonist hormone therapy (e.g. Lupron) and cardiovascular (CV) toxicity, and the mechanism by which CV risk-reduction is achieved by the novel oral GNRH-antagonist, relugolix. This objective will be studied using imaging and blood biomarkers.
Secondary Objective(s)	Identify genomic alterations that predispose an individual to enhanced CV toxicity following hormone therapy with GNRHa or relugolix
Research Intervention(s)/Interactions	A) GNRHa versus relugolix [randomization] B) Parallel, non-interventional cohort of men receiving no hormone therapy
Study Population	Men >18 years with localized intact or recurrence prostate cancer undergoing radiation therapy (with or without prior prostatectomy), with or without hormone therapy
Sample Size	90 men (30 men in GNRHa arm, 30 men in relugolix arm, 30 men in non-hormone therapy cohort)
Study Duration for individual participants	12 months
Study Specific Abbreviations/Definitions	Radiation therapy (RT) Androgen deprivation therapy (ADT) Gonadotropin-releasing hormone agonist (GNRHa) Gonadotropin-releasing hormone antagonist (GNRHaa) Nonsteroidal anti-androgen (AA) Combined androgen blockade (CAB) Major adverse cardiac events (MACE)
Funding Source (if any)	Prostate Cancer Foundation-Pfizer-Myovant Challenge Award, Prostate Cancer Foundation Young Investigator Award

2. Objectives

Androgen deprivation therapy (ADT) with a gonadotropin-releasing hormone agonist (GNRHa) is a highly effective and commonly used treatment for prostate cancer (PCa) with over 500,000 men with PCa receiving ADT annually in the United States^{3,4}. However, large observational studies suggest GNRHa is associated with increased risk of myocardial infarction (MI) and sudden cardiac death, raising concerns that ADT causes cardiovascular (CV) harm⁴⁻⁶. In fact, as more men survive PCa due to increasing ADT use, **CV**

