Aim 2.1: To determine how pre-existing and ADT-augmented inflammatory immune responses impact CV toxicity, we will evaluate pre-treatment, 3-, 6-, and 12-month peripheral blood mononuclear cells (PBMC) samples from all patients enrolled on trial. We will first evaluate the frequency and function of inflammatory immune populations by flow cytometry. While we will include a comprehensive panel evaluating lymphocyte and myeloid populations, we will specifically conduct an in-depth analysis quantifying the frequency, phenotype, and activation of T cells and macrophages. In particular, we will evaluate the frequency of naïve (CD44-CD62L+), effector memory (CD62L^{lo}CCR7-CD27^{lo/int}), central memory (CD62L^{hi} CCR7^{hi} CD44^{hi}), CD4 T-helper subsets (staining for the transcription factors Tbet, EOMES, ROR γ , and GATA), and CD4+ Tregs cells (CD25+GITR+CD127-Foxp3+)⁴⁷. Circulating macrophages will be evaluated for inflammatory M1 (CD80, CD86) and immunosuppressive M2 (CD163, CD206) sub-populations. Immune cells will also be evaluated for expression of GNRH receptors, as well as function by expression of intracellular cytokines associated with T cell activity (including IFNy, TNF α , IL-2, IL-4, IL-6, IL-10, and Granzyme B as we have published^{48,49}) or macrophage activity (Arg1, TNF σ , IL-6, IL-12).

Protocol Title: Mechanism and Predictors of Cardiotoxicity after Prostate Cancer Treatment: A Parallel Cohort and Randomized Trial Comparing Radiation Alone, Radiation plus Leuprolide, and Radiation plus Relugolix

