In addition to evaluating peripheral immune populations, plasma will be isolated at the same timepoints and evaluated for chemokine and cytokine production by multiplex assay (Human Cytokine/Chemokine/Growth Factor 71-Plex Clinical Assay, Eve Technologies). This assay measures both inflammatory and suppressive chemokines and cytokines, as well as growth factors involved in cardiac activity. Factors found to be altered via multiplex (either following ADT, between treatment groups, or between patients who develop CV toxicity) will be validated by ELISA. Finally, to evaluate the mechanistic significance of these alterations, human cardiac myocytes (the AC16 cell line and primary cardiomyocytes (Sigma Aldrich)) grown under wild-type or androgen-deprived conditions will be evaluated for altered expression of these factors by ELISA. Supernatants from these cells will be used in transwell migration assays to evaluate how androgen deprivation-induced alteration of these factors impacts the migration of T cells, macrophage, or other relevant immune populations across a transwell. Follow-up experiments will be conducted in which altered factors are either blocked or restored (recombinant protein) to determine if these factors are sufficient to alter immune migration towards cardiac cells.

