Aim 2.2: To determine how proteomic biomarkers associated with inflammatory immunity correspond with CV toxicity following ADT, we will conduct in-depth proteomic profiling, which has previously been utilized and validated to identify signatures associated with inflammatory immune responses and cardiovascular risk^{50,51}. To evaluate whether these signatures are associated with CV toxicity following ADT using leuprolide but not relugolix, pre-treatment and 12-month post-ADT PBMC will be subjected to proteomic profiling in conjunction with the Emory Integrated Proteomic Core as published by our colleagues at the Winship Cancer Institute⁵². Using nanocapillary liquid chromatography coupled with tandem mass spectrometry, this technology will be used to analyze patient PBMC samples for highly sensitive protein identification, posttranslational site mapping, and protein quantification. Briefly, PBMCs will be thawed under controlled conditions, sonicated in the presence of lysis buffer, protease inhibitors and phosphatase inhibitors. Protein samples will be sequentially digested, desalting, and dried under vacuum. Following reconstitution, samples will be loaded and eluted from a silica column driven by a UPLC system, monitoring elution spectra on a Fusion Mass Spectrometer. The mass spectrometry scans will be collected at a resolution of 120,000 at m/ 200 in profile mode while in a higher-energy collision dissociation fragmentation MS/MS spectra. Following sequencing, the combined *Homo sapiens* UniProt subsets will be used as references for proteomics searches. Data will be normalized to account for systematic differences in protein signal distributions, by aligning the medians of the log₂ protein signal distributions. Pathway enrichment will be conducted using gene sets obtained from the KEGG Pathway and MSigDB databases.

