Analysis Plan: Immune responses (e.g., frequency or function of immune populations) and circulating proteomic biomarkers will first be summarized and plotted by the follow-up time points to illustrate the change pattern over time for all patients and then separated by treatment arms. We will first test whether these biomarker change pattern would be altered by treatment groups (e.g., GNRH-agonist versus GNRH-antagonist) using Kruskal-Wallis test, and then we will link such pattern (e.g., percentage change from baseline for biomarkers) with related CV injury metrics as in Aim 1 using the similar statistical strategy as in Aim 1.2. P-value will be adjusted for multiple testing using Holm-Bonferroni method to control familywise error rate.

Aim 3: To determine how pre-existing genomic alterations promoting inflammatory immunity impact development of CV toxicity following GNRHa versus relugolix, pre-treatment PBMC samples will be subjected to whole exome sequencing to determine alterations to the protein-coding regions of the genome. DNA will be extracted from PBMC and analyzed for quality. Following this analysis, DNA will be fragmented using restriction enzymes and undergo a second round of quality control. Fragmented DNA will be used to generate next-generation sequencing libraries and will undergo capture for exomic DNA sequences (Illumina Nextera Rapid Capture Expanded Exome), followed by amplification and repeated QA/QC. DNA sequencing will be conducted using the Illumina HiSeq platform. The FASTQ data files will be aligned using BWA-MEM, and variants from the human genome will be determined using VarScan and annotated using ANNOVAR. To be considered a valid mutation it will need to comprise at least 2% of the reads, as has been utilized to identify CHIP-related mutations^{27,55}.

Protocol Title: Mechanism and Predictors of Cardiotoxicity after Prostate Cancer Treatment: A Parallel Cohort and Randomized Trial Comparing Radiation Alone, Radiation plus Leuprolide, and Radiation plus Relugolix

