Analysis Plan: The correlation among baseline genomic biomarkers, inflammatory biomarkers, and proteomic biomarkers will be described using Spearman Correlation Coefficient for all patients and by treatment group separately. The association of genomic alterations with CV injury metrics (as defined in Aim 1) will be handled by similar statistical strategy as in Subaim 1.2. Additionally, the association of genetic aberrations with peripheral immune responses (as in Aim 2) will be carried out by similar statistical strategy as in Aim 2.

Other statistical considerations:

Safety Population: All patients receiving at least one dose of GNRHa or Relugolix (for parallel randomized arms) or radiation alone (for parallel single cohort arm) will be considered evaluable for safety analyses.

Intent-to-Treat Population: Patients who are evaluable for safety and who are furthermore evaluable at 12-month CCTA assessment will be considered evaluable for correlative biomarker analyses.

Safety Analysis: All AEs experienced data will be described by summary statistics. Adverse events will be assessed according to CTCAE version 5.0 and will be evaluated by grade, attribution, and organ class. Adverse event listings and tabulated summaries of categorized AEs will be generated for all patients collectively and will be summarized by arms. Vital signs and laboratory data will be summarized for changes over time on study.

Stopping Rule: The two ADT test agents are FDA-approved drugs that are used in clinical practice, and hence no stopping rule for safety is in place officially.

7. Data Specimen Banking

To achieve Aims 2 and 3 discussed above, peripheral blood specimens will be collected longitudinally four times for each enrolled patient (i.e. pre-treatment, 3 months, 6 months, 12 months).

Draw 1 (pre)	Draw 2 (3mo)	Draw 3 (6mo)	Draw 4 (12mo)
Pre-ADT	2-4 months post-ADT initiation	6-8 months post-ADT initiation	12-15 months post-ADT initiation

The blood is collected and processed according to the standard operating practices and regulatory parameters of the Winship biorepository and under the guidance of a board-certified pathologist.

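### The Aim 2 Kruskal-Wallis test leaves the tested variable and the groups undefined and cannot adjust for baseline; a baseline-adjusted comparison of the two randomised arms would serve the aim better

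*Combined protocol and SAP*

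**What the plan says.** Section 6, Aim 2.1, on flow cytometry: "we will evaluate pre-treatment, 3-, 6-, and 12-month peripheral blood mononuclear cells (PBMC) samples from all patients enrolled on trial". For cytokines, "plasma will be isolated at the same timepoints and evaluated for chemokine and cytokine production by multiplex assay". Section 7 confirms that "peripheral blood specimens will be collected longitudinally four times for each enrolled patient". Proteomics (Section 6, Aim 2.2) has two time points only: "pre-treatment and 12-month post-ADT PBMC will be subjected to proteomic profiling".

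In the Aim 2 analysis plan the biomarkers "will first be summarized and plotted by the follow-up time points to illustrate the change pattern over time for all patients", and then by arm. The single between-group test follows: the team will "test whether these biomarker change pattern would be altered by treatment groups (e.g., GNRH-agonist versus GNRH-antagonist) using Kruskal-Wallis test". The next step is to "link such pattern (e.g., percentage change from baseline for biomarkers) with related CV injury metrics as in Aim 1", using a strategy attributed to Aim 1.2 that Section 6 does not set out. P-values are Holm-Bonferroni adjusted.

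The plan names no visit or summary measure for the test, no group-by-time term, no baseline covariate and no pairwise follow-up. Section 6 stratifies the randomisation by ASCVD risk, but the Aim 2 analysis does not use the stratum.

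**The concern.** Aim 2 asks whether agonist and antagonist differ in the immune response that follows ADT. Three features of the named test fit that question poorly.

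- **The variable is open.** Kruskal-Wallis compares one number per independent patient. A pattern over three follow-up visits must first become one number, and the plan does not say which. The choice could be made after the scheduled plots have been seen.
- **No covariates.** A rank test on change uses baseline by subtraction or division, which is usually less efficient than adjusting for it. The ASCVD stratum cannot enter at all.
- **The groups are open.** Agonist versus antagonist appears only as an example. With the non-randomised no-ADT cohort included, the test is an omnibus one and can reject although the two drugs act identically.

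Factors found altered go on to ELISA validation and laboratory experiments (Section 6, Aim 2.1), and Aim 3 reuses the Aim 2 strategy. An ambiguous or weak first test therefore carries forward.

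**Working it through.** Aim 2 states no effect size, power or alpha, so there is no plan figure to reproduce.

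**From the documents.** Section 1 gives "90 men (30 men in GNRHa arm, 30 men in relugolix arm, 30 men in non-hormone therapy cohort", so n = 30 per group and 60 randomised men. Flow cytometry and cytokines have one baseline and three follow-up draws.

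**Assumed.** Normal data with SD 1, equal correlation ρ = 0.4/0.6/0.8 between any two visits, a 0.5 SD difference between the drugs, two-sided 5%, one marker, no missing data. Simple change stands in for percentage change.

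**Step 1: per-patient variance of each analysis.**
- Change at 12 months: 2(1 − ρ) = 1.20/0.80/0.40.
- Baseline-adjusted at 12 months: 1 − ρ² = 0.84/0.64/0.36.
- Baseline-adjusted mean of three visits: (1 + 2ρ)/3 − ρ² = 0.44/0.373/0.227.

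**Step 2: normal-theory power**, Φ(δ√(15/v) − 1.96), where 15 = 30/2. At ρ = 0.4 and δ = 0.5:
- Change: 0.5 × √(15/1.20) − 1.96 = −0.19, power 42%.
- Adjusted at 12 months: 0.5 × √(15/0.84) − 1.96 = 0.15, power 56%.
- Adjusted mean: 0.5 × √(15/0.44) − 1.96 = 0.96, power 83%.

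**Step 3: simulated power of the actual tests, constant effect.**

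| Analysis | ρ = 0.4 | 0.6 | 0.8 |
|---|---|---|---|
| Kruskal-Wallis, 12-month change | 40% | 54% | 85% |
| Baseline-adjusted, 12 months | 54% | 66% | 88% |
| Kruskal-Wallis, mean follow-up minus baseline | 56% | 71% | 95% |
| Baseline-adjusted mean of three visits | 82% | 86% | 98% |

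The simulated figures sit close to Step 2; repeat runs agree within about three points. For the same summary, adjustment gains 14/12/3 points at 12 months and 26/15/3 points for the mean.

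**Step 4: effect shape.** If the effect is 0/0.25/0.5 SD at 3/6/12 months, the mean effect is (0 + 0.25 + 0.5)/3 = 0.25 SD. At ρ = 0.4, 0.25 × √(15/0.44) − 1.96 = −0.50, or 31%. Simulation gives 28/34/52% for the adjusted mean, against 39/53/84% for Kruskal-Wallis on 12-month change. If the effect fades (0.5/0.25/0), the mean is again 0.25 SD, but month 12 has nothing to detect.

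**Step 5: three groups of 30, both drugs shifted 0.8 SD from no ADT.** The chance that a treated man exceeds an untreated one is Φ(0.8/√2) = 0.714. The no-ADT mean rank is 15.5 + 60 × 0.286 = 32.65, which is 12.85 below the overall 45.5; each drug arm is 6.43 above it. The noncentrality is 12/(90 × 91) × (30 × 12.85² + 60 × 6.43²) = 10.9. On 2 degrees of freedom that gives about 85% rejection; direct simulation gives about 88%. In runs with equal shifts of 0.667 and 1 SD, the three-group test rejected in 71% and 98%, and the direct agonist-antagonist test in only 4.4% of both.

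**The case against.** A rank test for many possibly skewed markers at 30 per arm is defensible, and Section 2 calls Aim 2 secondary and correlative. That stands. It limits how much weight the point carries, but it does not supply the missing definitions.

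Several stronger readings are tempting, and the documents do not support them:

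- **Baseline is discarded.** The pattern is exemplified as percentage change from baseline, so baseline is used, though not as a covariate.
- **The test must be repeated at each visit.** One summary per patient gives a single valid test, and Step 3 shows that much of the gain comes from the summary chosen.
- **The test certainly has three groups.** The only comparison named is agonist versus antagonist. With two groups, Kruskal-Wallis is the two-sided Wilcoxon rank-sum test and does isolate that contrast. Step 5 is conditional.
- **Type I error is inflated.** Uncorrected visit-by-visit testing would give about 12–13%, but the plan specifies Holm. Nothing suggests that visits would be pooled as independent observations.
- **Every marker has four visits.** Proteomics has two.
- **Averaging over visits always wins.** Step 4 shows that it does not. ADT lasts 6–24 months (Section 6), so some men may be off drug at month 12, and the shape of the effect is unknown.

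The single-marker powers are also optimistic for a 71-marker panel. At the first Holm step (0.05/71 = 0.0007) the adjusted mean has roughly 32/41/75% by normal approximation.

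**Conclusion.** The point holds as a matter of under-specification and efficiency. The named test is valid once its variable and groups are fixed, but the plan fixes neither, and a better method exists for data already being collected. For the same summary, baseline adjustment has more power than Kruskal-Wallis on change: 3 to 14 points at 12 months, and 3 to 26 points for the three-visit mean under a constant effect. The gain is largest at low correlation. The further gain from averaging depends on the effect shape and cannot be promised. A significant result that includes the no-ADT cohort would not show an agonist-antagonist difference. All sizes rest on the assumed 0.5 SD effect, equal correlations, normal data and one marker at two-sided 5%; the documents give no Aim 2 values to replace them.

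**What to change.** In the Aim 2 analysis plan:

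1. Make GNRHa versus relugolix in the 60 randomised men the primary contrast. Report the non-randomised no-ADT cohort separately.
2. For flow cytometry and cytokine markers, fit a longitudinal model on the log scale (on ranks for skewed markers) with arm, visit, arm-by-visit, baseline value and ASCVD stratum.
3. Before data are seen, name one lead contrast: the average over 3, 6 and 12 months, or month 12. Base the choice on the expected course of the effect.
4. For proteomics, use baseline-adjusted ANCOVA at 12 months.
5. Keep Holm across markers, and keep a two-arm rank test as a sensitivity analysis.

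This needs no new samples or patients. It costs SAP wording, modest programming and a distributional assumption, which the log or rank scale and the sensitivity test ease.

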Analysis Plan: We will measure coronary plaque volume using CCTA images at both baseline and 12-months post-treatment initiation. The primary endpoint will be (1) total coronary plaque volume (continuous). Secondary endpoint will be non-calcified coronary plaque volume (continuous). Other outcome measures include (1) calcified plaque volume (continuous), (2) low-attenuation plaque volume (continuous), (3) coronary artery calcification score (continuous), and (4) coronary vessel stenosis (ordinal). The change in endpoint metrics between baseline and 12-month will be estimated for leuprolide versus relugolix versus no ADT. Data transformation to fit statistical assumptions will be done as needed. In addition, we will implement multivariable models that control for potential confounders (e.g. age, statin medication use) using general linear regression and/or logistic regression.

Power: We hypothesized that there will be significantly greater total plaque burden (i.e. summation of total plaque volume of all major coronary territories) increase from baseline to month 12 following GNRHa versus no ADT or relugolix. Using a standard deviation of 30 mm³ for the change in total plaque volume from scans obtained at two time points approximately 12 months apart in the study, 60 participants (30 in each comparative treatment arm) with both baseline and month 12 CCTA would provide 80% power to detect a difference of ≥ 20 mm³ in the change in total plaque volume [$P(X>Y) 0.72$] from baseline to 12 months.

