Subaim 1.1. Relationship between ADT and accelerated coronary plaque development/rupture									
Subaim 1.2. How baseline cardiac imaging biomarkers correlate with ADT-associated plaque development									
Aim 2. Relationship between leuprolide versus relugolix on immune effector responses implicated in atherosclerosis									
Subaim 2.1. How pre-existing and ADT-augmented inflammatory immune responses impact CV toxicity									
Subaim 2.2. How circulating proteomic biomarkers predict for cardiac toxicity									
Aim 3. How pre-existing genomic alterations impact development of cardiac toxicity following leuprolide versus relugolix									
Subaim 3.1: Identification of how pre-existing genomic alterations impact immune responses and CV toxicity									

10. Inclusion and Exclusion Criteria

Inclusion:

- Men ≥18 years old
- Non-metastatic prostate cancer
- Non-metastatic, biochemically recurrent prostate cancer
- Plan to undergo curative-intent pelvic radiation therapy (photons or protons) with or without brachytherapy

Exclusion:

- Metastatic prostate cancer requiring >24 months of ADT
- Prior invasive cancer diagnosis
- Prior exposure to androgen deprivation therapy
- Prior exposure to chemotherapy, immunotherapy, or radiation therapy

Protocol Title: Mechanism and Predictors of Cardiotoxicity after Prostate Cancer Treatment: A Parallel Cohort and Randomized Trial Comparing Radiation Alone, Radiation plus Leuprolide, and Radiation plus Relugolix

- History of cardiac bypass surgery, percutaneous coronary intervention, or cardiac device implantation
- Renal insufficiency, contrast allergy, or arrhythmias that limits feasibility of CT acquisition

11. Vulnerable Populations

Not applicable. This study does not involve individuals who are vulnerable to coercion or undue influence, such as pregnant women, children/minors, cognitively-impaired, prisoners, etc.

12. Local Number of Participants

Our accrual goal for this protocol is 90 patients (n=30 in each arm).

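### The Aim 2 link between biomarker response and plaque names only percentage change from baseline and no baseline adjustment, so it cannot separate pre-existing from ADT-augmented immunity

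*Combined protocol and SAP*

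**What the plan says.** All of this is in section 6 (Procedures Involved) unless noted.

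- **Group comparison, Aim 2.** The plan first tests whether biomarker change patterns are "altered by treatment groups (e.g., GNRH-agonist versus GNRH-antagonist) using Kruskal-Wallis test". This step is rank-based.
- **Link to plaque, Aim 2.** It will then "link such pattern (e.g., percentage change from baseline for biomarkers) with related CV injury metrics as in Aim 1". For the method, the plan sends the reader to another subaim, whose approach is to be copied: "using the similar statistical strategy as in Aim 1.2". Adjustment is by Holm-Bonferroni; neither the significance level nor the family of tests is stated.
- **Aim 1.2.** No analysis plan for it appears. Section 9 (Study Timelines) carries only a title line: "Subaim 1.2. How baseline cardiac imaging biomarkers correlate with ADT-associated plaque development".
- **Aim 1 Analysis Plan.** The only modelling described is multivariable, "using general linear regression and/or logistic regression". Age and statin use are given as example covariates; baseline biomarker level is not mentioned. A general clause allows data to be transformed when assumptions require it.
- **Proteomics, Aim 2.2.** Signals are normalised "by aligning the medians of the log₂ protein signal distributions". The scale for analysing change is not stated.
- **What Aim 2 asks.** Aim 2.1 asks about both pre-existing and ADT-augmented immune responses. Section 4 adds the hypothesis that pre-existing inflammation raises the risk of CV injury after ADT.

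Blood is drawn at baseline and at 3, 6 and 12 months. The plan does not say which follow-up draw defines the change, or how a zero or undetectable baseline is handled, although 71 plasma analytes are assayed.

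**The concern.** Percentage change is follow-up divided by baseline, minus one. A man with a high baseline tends to show a fall and a man with a low baseline a rise, through regression to the mean alone. If baseline inflammation predicts plaque growth, as the protocol hypothesises, percentage change will correlate with plaque growth even when the change itself carries no information. A baseline effect could then be reported as a treatment-induced immune effect, or a real induced effect could be masked.

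Division by baseline also makes the metric unstable. For a skewed cytokine or a rare cell subset, a few men with very low baselines can determine the regression slope, and the metric is undefined at zero. The Kruskal-Wallis step gives no protection here, because the link to plaque is a separate analysis.

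**Working it through.** The plan states no power, effect size or error rate for the Aim 2 link, so there is no figure to reproduce. Its only power statement concerns the plaque comparison and does not bear on this point.

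**Assumed inputs (none is in the documents).** Log-normal biomarker with log-SD s = 0.5, 1.0 or 1.5; within-man correlation on the log scale ρ = 0.5; plaque change depends only on the measured log baseline, r = 0.4; n = 60 (the two randomised arms); two-sided 0.05 before Holm. Any significant change–plaque result is then a misattribution.

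**Step 1: coupling to baseline.**
- Log ratio: corr(log ratio, log baseline) = −√((1−ρ)/2) = −0.50.
- Percentage change: corr = −s(1−ρ)/√(exp(2s²(1−ρ)) − 1).
  - s = 0.5: −0.25/0.533 = −0.47
  - s = 1.0: −0.50/1.311 = −0.38
  - s = 1.5: −0.75/2.913 = −0.26

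**Step 2: induced correlation with plaque.** Multiply by 0.4. The log ratio gives −0.20. Percentage change gives −0.19, −0.15 and −0.10.

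**Step 3: false-significance rate.** Approximately Φ(atanh|r|·√(n−3) − 1.96).
- Log ratio: 0.203 × 7.55 = 1.53; Φ(−0.43) = 33%.
- Percentage change, s = 0.5: 0.190 × 7.55 = 1.43; Φ(−0.53) = 30%.
- At larger s the formula is too low, because 60 men rarely include the extreme tail that drives the population value. Simulation is used instead.

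| Analysis | s = 0.5 | s = 1.0 | s = 1.5 |
|---|---|---|---|
| Percentage change, unadjusted | 30% | 25% | 19% |
| Log ratio, unadjusted | about 33% | about 33% | about 33% |
| Log follow-up adjusted for log baseline | about 5% | about 5% | about 5% |

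Spearman correlation on percentage change gave about 30%, so ranks do not remove the problem.

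**Step 4: why adjustment works here.** The numerator of the partial correlation of follow-up with plaque given baseline is ρr − ρ·r = 0.20 − 0.5 × 0.4 = 0, so the test keeps its level.

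**Step 5: sensitivity.** Aim 2.1 samples all 90 planned men. At n = 90 the log-ratio rate is Φ(0.203 × √87 − 1.96) = Φ(−0.07) = 47%, so more men make it worse. Holm lowers the rate but does not remove the bias. With an assumed family of 71, the first threshold is 0.05/71 = 0.0007 (z = 3.39). For percentage change at s = 0.5 the rate is Φ(1.43 − 3.39) = 2.5%, some 35 times nominal.

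**Step 6: instability.** In simulation at the same three spreads, the three most extreme of 60 men supplied a median 40, 61 and 77% of the variation in percentage change, against 26% for the log ratio. With no shift in the median and s = 1.0, the mean percentage change was +64% at ρ = 0.5 and +35% at ρ = 0.7.

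**The case against.** Several counter-arguments are sound and limit the point.

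- **Percentage change is only an example.** This stands. A reader might infer that the metric is fixed; the text does not say so. But no alternative and no baseline covariate is offered.
- **The transformation clause in Aim 1 might carry over.** It might, and it would permit logs. It would not supply baseline adjustment, and an unadjusted log ratio is just as coupled to baseline.
- **The group comparison is not harmed by the choice between percentage change and log ratio.** This stands. One is a monotone function of the other, so Kruskal-Wallis returns the same statistic. A power loss computed from a t-test on percentage change would concern a test that is not planned.
- **A reader might infer that percentage change inflates false positives generally.** It does not. With no link of plaque to either baseline or change, rejection stayed at about 5%.
- **A reader might infer a definite loss of power.** That depends on the assumed truth. For n = 60 and a true correlation of 0.35:
  - If plaque follows follow-up given baseline, percentage change has 50–72% power against 78–80% for the adjusted log model.
  - If plaque follows the log change, percentage change has 63–79% and an unadjusted log ratio 78–80%. The adjusted model has about 67–72% at log-SD 0.2–0.3, where percentage change has 76–79%.
  - If plaque follows percentage change itself, that metric has 67–80% and the adjusted model 43–72%.
- **A reader might infer that percentage change is meaningless for proteomics.** This holds only if percentages are taken on log2 values, where one doubling is 5% of a value of 20 but 50% of a value of 2. On back-transformed signals a doubling is always +100%. The protocol names log2 for normalisation only.
- **Logs also fail at zero**, for example for rare cell subsets. This stands, so the remedy needs a stated rule.

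**Conclusion.** The point holds as a defect in a secondary analysis. The only metric named for the biomarker–plaque link is coupled to baseline, no baseline covariate is stated, and the cited strategy is not described. Aim 2 cannot separate pre-existing from augmented immunity on that basis. Under the stated assumptions, misattribution occurs in about 19–30% of trials with unadjusted percentage change, about 33% with an unadjusted log ratio, and about 5% with baseline-adjusted log follow-up.

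These sizes are illustrative, since biomarker spread, within-man correlation and effect are all assumed. They also assume that plaque depends on the measured baseline. At the opposite extreme, suppose both readings are noisy measures of one stable level that drives plaque (r = 0.4), again with ρ = 0.5. Each reading then correlates 0.4 × √0.5 = 0.283 with plaque. The partial correlation of follow-up given baseline is (0.283 − 0.5 × 0.283)/√(0.75 × 0.92) = 0.17, so the adjusted model is itself significant in about Φ(0.172 × √56 − 1.96) = 25% of trials. The change score then has zero correlation with plaque. Adjustment addresses regression to the mean around the measured baseline; it does not remove assay error. This is a further reason to fix the model and its interpretation in advance.

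Section 2 describes Aim 2 as secondary correlative work. The primary comparison of plaque volume is not affected.

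**What to change.** In the Aim 2 linking regressions:

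- Replace percentage change with the log2 follow-up value and include the log2 baseline value as a covariate. A log ratio gives the same response coefficient only if log baseline is also in the model.
- Name the follow-up time point that defines the response.
- State one rule for zero or undetectable values, covering cell-subset frequencies as well as cytokines.
- For proteomics, analyse on the log2 scale with the same baseline covariate.
- Write the model out in the Aim 2 plan instead of citing Aim 1.2.
- Back-transform and report as fold change.

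The cost is SAP wording, a little analysis work and one degree of freedom per model. Power is lost if plaque truly tracks raw percentage change, and can be lost if it tracks the pure log change. No new patients, samples or assays are needed, because the baseline value is already collected.
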